4.2.10 Calculation of change

Baseline value will be the value collected during the baseline assessment as per the specific definition applying to the parameter, e.g. lab value

Absolute change from baseline will be the absolute difference between value a time point t (post-baseline) and value at baseline assessment, it will be calculated as:

- Absolute change from baseline = post-baseline value – baseline value

Relative change from baseline, or Percentage change from baseline, will be calculated as:

- Relative change from baseline (%) = (absolute change / baseline value) × 100

4.2.11 Visit Windows

A year = 365.25 days.

A month = 365.25/12=30.4375 days.

Month 1 = Day (1;45] and then floor(n×30.4375) days±15 days, n=2, 3, 4,... that is Month 2 = Day (45;75]; Month 3 = Day (75;106]; etc.

For each parameter (i.e., hematologic and erythroid response), time windows will be used to identify data to be considered for the specific analysis at a specific time point. If there is more than one assessment within the time window, the last available assessment in that time window will be used. For all windows after baseline, only values after first dose of study drug will be used. Time windows are defined based on date of randomization (=study day 1; Visit 3 according to VES of protocol).

The following table shows the time windows for the analyses of responses based on planned assessment schedule.

Table 4-1 Visit windows

Planned assessment	Time window	Nominal day for visit
Baseline	Baseline; see definition 4.2.6	Baseline
Visit 3: Date of Randomization	Day 1	Day 1
Visit 4	Day 4 to Day 10*	Day 7
Visit 5	Day 11 to day 17*	Day 14
Visit 6	Day 18 to Day 24*	Day 21
Visit 7	Day 25 to Day 31*	Day 28
Visit 8	Day 35 to Day 49*	Day 42
Visit 9	Day 50 to Day 63*	Day 56
Visit 10	Day 77 to Day 91*	Day 84
Visit 11	Day 105 to Day 119*	Day 112
Visit 12	Day 133 to Day 147*	Day 140

The End of Treatment visit time window is Day 161 to Day 175 with nominal day of visit is Day 168 considering Visit 3 as Day 1.

In case of early treatment discontinuation or end of visit 12, the follow up will be 27-33 days from the last date when a non-zero dose of study treatment is administered (Last date of study treatment).

Considering, a patient has received EPO only and received a response. This patient will hold EPO until study end. However, Follow-up visit for them will be 30 days (+/- 3 days after EOT) and not 27-33 days from the last date when a non-zero dose of study treatment is administered.

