2.9.1.1 Variable

The primary variable is the difference in proportion of patients achieving an erythroid response after 12 weeks of treatment between the two arms according to modified IWG 2006 criterion (increase in Hb from baseline ≥ 1.5 g/dL).

Patients meeting the criterion at any time within the first 12 weeks period will be considered erythroid responders.

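### The visit-window rule in SAP 4.2.11 is not reconciled with the any-time definition of erythroid response, and the last day of the 12-week period is not fixed

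*SAP*

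**What the plan says.** **Primary rule.** SAP 2.9.1.1: "Patients meeting the criterion at any time within the first 12 weeks period will be considered erythroid responders". SAP 2.9.1.2 and protocol 10.4.1 and 10.4.2 give the same rule: an Hb increase from baseline of at least 1.5 g/dL. None of them adds a visit window or a one-value-per-visit condition.

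**Window rule.** SAP 4.2.11: "For each parameter (i.e., hematologic and erythroid response), time windows will be used to identify data to be considered for the specific analysis". The sentence then refers to a specific time point. The section continues: "If there is more than one assessment within the time window, the last available assessment in that time window will be used". It introduces Table 4-1 with: "The following table shows the time windows for the analyses of responses based on planned assessment schedule".

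**Anchor and boundaries.** "Time windows are defined based on date of randomization (=study day 1; Visit 3 according to VES of protocol"). Visit 7 is "Day 25 to Day 31", Visit 8 is "Day 35 to Day 49", Visit 9 is Days 50 to 63 and Visit 10 is Days 77 to 91 with nominal Day 84. After the table: "The End of Treatment visit time window is Day 161 to Day 175".

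**A second set of windows.** The same section also defines month windows, which are contiguous and have different boundaries. They are not the ones named for the analyses of responses.

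**Hb schedule.** Protocol 7.2.2.4.1 and Table 7-1 place post-baseline Hb up to week 12 at Visits 5, 7, 8 (only after an EPO increase at Visit 7), 9 and 10. Table 7-1 labels Visit 10 as week 13.

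**The concern.** The any-time rule uses every Hb value in the period. The window rule discards values that fall between windows, and within a window it keeps the last value even if an earlier one met the threshold. The window text names erythroid response and presents its table as the one for responses, yet the SAP does not say which rule prevails or what happens to a value on an uncovered day. Neither section names the last day of the 12-week period.

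Erythroid response is the primary variable, and the difference in its proportion is the only between-arm interval in the plan. The trial is open-label and the trial team is unblinded (SAP 3.3), so the rule should be settled in writing before responders are counted.

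**Working it through.** The plan gives no figure on this point to reproduce. The check lists the windows, applies both rules to the same constructed data, and then sizes one change.

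**1. Days in no window (Table 4-1, Day 1 = randomization)**
- Before Visit 4 (Days 4-10): Days 2-3, 2 days. No haematology is scheduled then, so this gap has no practical effect.
- Between Visit 7 (to Day 31) and Visit 8 (from Day 35): Days 32-34, 3 days.
- Between Visit 9 (to Day 63) and Visit 10 (from Day 77): Days 64-76, 13 days.
- Total to Day 84: 2 + 3 + 13 = 18 days; 18/84 = 21%.
- Days 92-104, 120-132 and 148-160 add 39, making 57 days to Day 175.

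**2. Both rules on the same Hb changes (g/dL)**

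The any-time rule is applied to Days 2-84. The window rule takes the last value in each window from Visit 4 to Visit 10. Values not shown are all below 1.5.

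| Constructed series | Any-time | Windows |
|---|---|---|
| All on nominal days; +1.6 on Day 56, +1.2 on Day 84 | responder | responder |
| +1.6 on Day 70 (no window), +1.3 on Day 84 | responder | non-responder |
| +1.6 on Day 52, +1.3 on Day 60 (both Visit 9 window) | responder | non-responder |
| Visit 8 on Day 42 +1.6, early Visit 9 on Day 49 +1.3 (both Visit 8 window) | responder | non-responder |
| +1.6 on Day 80, +1.4 on Day 88 (both Visit 10 window) | responder | non-responder |
| Visit 10 on Day 86 +1.6 only | non-responder if the period stops at Day 84 | responder |

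Each scheduled Hb on its nominal day (14, 28, 42, 56, 84) falls alone in its own window, so the rules then agree. Disagreement needs an early, late, repeat or unscheduled value.

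**3. End of the 12-week period**
- 12 × 7 = 84 days. Counting randomization as Day 1, a visit exactly 12 weeks later is Day 1 + 84 = Day 85.
- Table 4-1 gives Visit 10 nominal Day 84 and a window to Day 91, so Days 85-91 are inside the window.
- Whether the any-time rule includes Days 85-91 is not stated. An ordinary Visit 10 on Day 86 raises the question without any unscheduled sample.

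**4. Size of one change**
- About 60 patients at 1:1 gives 30 per arm. One patient is 1/30 = 3.3 percentage points.
- Illustration from the middle scenario of SAP 2.11 (40% reference, difference 30%): 12/30 against 21/30. The standard Agresti-Caffo interval uses p = (x + 1)/(n + 2), so 22/32 = 0.6875 and 13/32 = 0.40625, a difference of 0.281. SE = √(0.6875 × 0.3125/32 + 0.40625 × 0.59375/32) = 0.119. The 95% interval is 0.281 ± 1.96 × 0.119 = (0.047, 0.515).
- One combination-arm responder reclassified (20 v 12): (0.013, 0.487). Two reclassified (19 v 12): (-0.020, 0.458).
- SAP 2.11 prints (0.068, 0.53) for this scenario. The standard formula does not return that interval; this is a separate matter and does not affect the comparison here.

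These intervals show sensitivity if the changes fall in one arm only. They are not a forecast of how many patients change.

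**The case against.** The strongest reply is that there is no real conflict. The window sentence is limited to analysis at a specific time point, and the primary endpoint is not of that kind: its any-time definition appears in four places across the two documents. By-visit summaries that need windows do exist (SAP 2.9.2.4 and 2.9.2.5), and a specific endpoint definition would normally override a general convention. On scheduled data the rules agree. Derivations are to be specified in RAP Module 8 (SAP 1.1), which is not available here, and the windows for Visits 4 to 12 carry an asterisk whose footnote is not in the text available and might qualify them. The study is a pilot without a formal sample size calculation.

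Much of this stands. The by-visit reading is possible and may be what was meant. It is not stated, however: the section names erythroid response and calls Table 4-1 the windows for the analyses of responses. Off-schedule Hb values are also foreseeable. Protocol 7.1.3 asks for end-of-treatment assessments as soon as possible after discontinuation, and 6.3.3 requires weekly follow-up when treatment stops for an adverse event or abnormal laboratory value.

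A reader might go further in three ways that the documents do not support:
- **That a large share of week-12 data is lost.** With visits spread evenly within 2 to 7 days of Day 85, 53-60% of Visit 10 values come after Day 84; around nominal Day 84 the share is 40-47%. Adding the assumption that 15-30% of responders first qualify at Visit 10 suggests a loss of 8-18% of responders. No section cuts the period at Day 84, Table 4-1 runs Visit 10 to Day 91, and the 15-30% has no source.
- **That early-termination Hb is always excluded**, because the only end-of-treatment window is Days 161-175. The windows are set by day, so such a value is selected if it falls on a covered day.
- **That the programmer would choose the rule.** Module 8 may already settle it.

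**Conclusion.** The point holds as an unresolved conflict between two stated rules on the primary endpoint, together with an undefined last day of the 12-week period. If the Table 4-1 windows were applied to responder status, Hb on Days 32-34 and 64-76 would be lost and a qualifying value could be overridden within its window, turning some any-time responders into non-responders. The Day 84, 85 or 91 question can also move classification the other way.

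The effect is confined to off-schedule or repeat values and to Visit 10 values after Day 84. How many patients that involves cannot be derived from the documents and may be few. Each one moves an arm by 3.3 points, assuming 30 per arm. The finding does not show that the primary result would be wrong, and with the number affected unknown it does not justify treating this as a critical defect. It warrants a specific correction to the SAP before analysis.

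**What to change.** In SAP 2.9.1.2 and 4.2.11, state that:
- responder status for the primary endpoint uses every Hb value after the first dose, scheduled or not, up to and including the Visit 10 assessment, with Day 91 as the latest day and, in patients who switch, no value after the first DFX dose;
- Table 4-1 and its last-value rule apply only to by-visit summaries.

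With this wording the gaps no longer affect the primary endpoint, so the windows need not be redrawn for it. A restriction to central-laboratory values or a closest-to-nominal-day rule is not needed to resolve the conflict. The cost is one SAP wording change and one derivation, with no new data.

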4.3 Data handling conventions

Partial dates will be listed as partial dates. For computing time/duration, the following rules will be used to impute partial dates: if the day and month is missing, it will be replaced by 30th of June (to be used only for prior events, e.g., medical history), if only the day is missing it will be replaced by 15th of that month. For dates known to be within the trial period, if this imputation makes the date later than trial completion date, then the trial completion date will be used; if the imputed date is earlier than the first medication date, then the first medication date will be used. The same rules of assigning AE start and end dates will apply for study medication start and end dates for subjects with missing or partial date of or with duplicate records of study medication.

Partially or completely missing AE onset dates and concomitant medication dates are imputed according to the standard Novartis imputation rules as described in the following:

Date imputation is the creation of a new, complete date from a partial one according to an agreed and acceptable algorithm. Missing date for AE will be handled according to STL standard.

A partial date is simply an incomplete date e.g.,
ddOCT2001 the days are missing from this DDMMYYYY date

Partial AEs start dates, if left partial, would ultimately mean the following

- It would not be possible to place the AE in time.
- Therefore the treatment/dosage at the time of the event would be unknown.
- Therefore the event could not be reported/summarized appropriately – if at all.

Therefore it is important to perform date imputation to ensure that as many data events are represented as correctly as possible. Of course partial and/or missing dates should *also* be caught as edit checks and passed back to the investigator for resolution.

There **will be no** attempt to impute the following:

- **Missing** AE start dates
- AE start dates **missing the year**
- Partial/missing AE **end dates**

Table 4-2 explains the abbreviations used.

Table 4-2 AE/Treatment Date Abbreviations

	Day	Month	Year
Partial Adverse Event Start Date	<not used>	AEM	AEY
Treatment Start Date (TRTSTD)	<not used>	TRTM	TRTY

Table 4-3 describes the possible combinations and their associated imputations. In the light grey boxes the upper text indicates the imputation and the lower text the relationship of the AE start date to the treatment start date (TRTSTD).

Table 4-3 Imputation algorithm

	AEM MISSING	AEM < TRTM	AEM = TRTM	AEM > TRTM
AEY MISSING	NC Uncertain	NC Uncertain	NC Uncertain	NC Uncertain
AEY < TRTY	(D) Before TRTSTD	(C) Before TRTSTD	(C) Before TRTSTD	(C) Before TRTSTD
AEY = TRTY	(B) Uncertain	(C) Before TRTSTD	(B) Uncertain	(A) After TRTSTD
AEY > TRTY	(E) After TRTSTD	(A) After TRTSTD	(A) After TRTSTD	(A) After TRTSTD

The legend to the above table is shown in Table 4-4.

Table 4-4 Relationship and Imputation Legend

Relationship	
Before TRTSTD	Indicates AE start date prior to Treatment Start Date
After TRTSTD	Indicates AE start date after Treatment Start Date
Uncertain	Insufficient to determine the relationship of AE start date to Treatment Start Date
Imputation Calculation	
NC / Blank	No convention/imputation
(A)	01MONYYYY
(B)	TRTSTD+1
(C)	15MONYYYY
(D)	01JULYYYY
(E)	01JANYYYY

Few examples are shown in Table 4-5.

Table 4-5 Example Scenarios

Partial AE start date	Treatment start date	Relationship	Imputation Calculation	Imputed Date
12mmyyyy	20OCT2001	Uncertain	NC	<blank>
ddmmm2000	20OCT2001	Before	(D)	01JUL2000
ddmmm2002	20OCT2001	After	(E)	01JAN2002
ddmmm2001	20OCT2001	Uncertain	(B)	21OCT2001
ddSEP2001	20OCT2001	Before	(C)	15SEP2001
ddOCT2001	20OCT2001	Uncertain	(B)	21OCT2001
ddNOV2001	20OCT2001	After	(A)	01NOV2001

For any continuing events (e.g. AEs, concomitant medication, etc) which needs to be summarized for annual reports (or any interim analyses), when a date cut-off date is used an indication in the listings will be done to inform that the event is continuing. For patients who discontinue the study with ongoing events, the discontinuation date will be used as the completion date of the event.

Vital sign, Study Completion, CMP, ECG and laboratory assessment dates will be imputed in associating visit date from Visit-based event date imputation (AVIS) (see RAP Module 8).

Any event which has a partial date and requires imputing but has no specific imputation rule will be described in the RAP Module 8 and the imputed will be as follows:

- If the day and month is missing, it will be replaced by 1st of July. If only the day is missing it will be replaced by the 1st of that month. Partial dates will remain partial in the data listings.
- Missing day information for start date of prior chelation therapy or start date of history of blood transfusions will be imputed by the 15th of the Month. If the month will be missing it will be imputed by July.

A missing category for categorical data will be presented where applicable. Unless otherwise noted, percentages will be based on the number of patients in the relevant population or subgroup.

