6.3.1.7 Dose modification criteria for hypersensitivity reactions

Cases of serious hypersensitivity reactions (such as anaphylaxis and angioedema) have been reported in patients receiving DFX, with the onset of the reaction occurring in the majority of cases within the first month of treatment. If reactions are severe, DFX should be discontinued and appropriate medical intervention instituted.

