2.2 Data included in the analyses

Data will be collected on patients aged ≥ 18 years or older with low- and-int-1-risk MDS, randomized in 1:1 ratio to DFX+EPO or EPO alone. If after 12 weeks of treatment with EPO alone, Hb increase is < 1 g/dL and total Hb is < 12 g/dL, the patient will switch to combination therapy of EPO and DFX. The study treatment duration is 24 weeks.

As per the current protocol, no interim analysis is planned. All interim (if required) and final CSRs will have a documented medical review by [REDACTED].

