2.10.2 Adverse events (AEs)

The reporting of AEs and AEs of special interest will be reported in the following periods based on the treatment received as follows:

- For patients receiving EPO during the first 12 weeks and for those continuing with EPO after 12 weeks (no switching to EPO+DFX arm), the safety data will be reported based on the corresponding treatment group: EPO. The safety data will be reported in period 1-12 weeks, 13-24 weeks and 1-24 weeks.
- For patients receiving EPO+DFX DT or EPO+DFX FCT from week 1 and continuing with EPO+DFX DT or EPO+DFX FCT after 12 weeks or with DFX DT or DFX FCT alone after 12 weeks, the safety data will be reported based on the corresponding treatment group EPO+DFX. The safety data will be reported in period 1-12 weeks and 1-24 weeks.
- For patients receiving EPO alone and switched to EPO+DFX after 12 weeks of treatment, the safety data will be reported only in period 13-24 weeks.

Overall summary will be reported for AEs occurred in period 1-12 weeks of treatments and 1-24 weeks for patients receiving EPO alone and patients receiving EPO+DFX DT or EPO+DFX FCT.

Overall summary, SAE and AEs leading to study drug discontinuation will be reported for in the corresponding treatment: EPO, DFX DT, DFX FCT, EPO+DFX DT and EPO+DFX FCT.

All AEs will be coded using the latest version of MedDRA at the time of analyzing data using the Safety Set. The severities of the AE will be coded as mild/moderate/severe as documented in the CRF.

Summary tables for AEs have to include only AEs that started or worsened during the on-study period, the treatment-emergent AEs, i.e. TEAEs. However, all safety data (including

those from the pre and post-study periods) will be listed and those collected during the pre-study and post-study period will be flagged.

If an AE deteriorates or improves over time, new event will be reported accordingly with new severity.

The incidence of treatment-emergent AEs (new or worsening from baseline) will be summarized by system organ class and or preferred term, severity (mild/moderate/severe), type of AE and relation to study treatment.

Deaths reportable as SAEs and non-fatal serious AEs will be listed by patients and tabulated by type of AE.

Additionally, AEs and SAEs with suspected relationship to study drug, requiring dose adjustment, leading to drug interruption/discontinuation, requiring significant additional therapy will be specifically tabulated and listed.

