4.2.2 Date of first administration of study treatment

The date of first administration of study treatment will be derived as the first date when a non-zero dose of study treatment will be administered. For the sake of simplicity, the date of first administration of study treatment is referred to **start date of study treatment**. Start date of study treatment is defined by first non-zero dose administration date of EPO or EPO+DFX DT or EPO+DFX FCT.

The date of first administration for EPO and EPO+DFX DT or EPO+DFX FCT will be recorded on the corresponding “dosage administration record” (DAR) eCRF page.

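### For patients switched from EPO to EPO+DFX, a month-only AE date in the month DFX starts is imputed to before the first DFX dose and can drop out of the weeks 13-24 tables

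*SAP*

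**What the plan says.** SAP 4.3 gives AE onset dates their own algorithm. Table 4-3 compares the AE's known month and year with the treatment start date, and each cell holds the imputation and "the lower text the relationship of the AE start date to the treatment start date (TRTSTD"). Table 4-4 supplies the dates. Rule (B), treatment start + 1, applies when the month, or the year alone, matches that of treatment start. Rule (A), the 1st of the known month, applies to any later known month. Rule (E), 1 January, applies to a later year with no month.

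The reference date is defined in SAP 4.2.2: "Start date of study treatment is defined by first non-zero dose administration date of EPO or EPO+DFX DT or EPO+DFX FCT". For a patient randomised to EPO alone, that is the first EPO dose.

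SAP 4.3 also says why dates are imputed. If a start date were left partial, the event could not be placed in time: "Therefore the treatment/dosage at the time of the event would be unknown".

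SAP 2.2 sets the switch: "If after 12 weeks of treatment with EPO alone, Hb increase is < 1 g/dL and total Hb is < 12 g/dL", the patient moves to the combination. Visit 10, the week 12 visit, has the window "Day 77 to Day 91" (SAP 4.2.11). For patients who switch, SAP 2.10.2 states that "the safety data will be reported only in period 13-24 weeks".

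**The concern.** Rule (B) keeps an AE of uncertain timing on the treated side of the first dose. A switcher has a second boundary, the first DFX dose, where no such rule operates. SAP 2.10.1 has a fallback for incomplete dates, but it settles only whether an event is pre-, on- or post-treatment. An AE near the switch is on-treatment either way.

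The stated purpose of imputation is to know the treatment at onset, and the rule fails at the point where treatment changes. What is at stake is the AE count for the first weeks on DFX in switchers. These weeks are informative: Protocol 6.3.1.7 describes serious hypersensitivity reactions to DFX "with the onset of the reaction occurring in the majority of cases within the first month of treatment". If the SAP 2.10.1 listing column for treatment at onset uses the imputed date, it would also show EPO alone.

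**Working it through.** **1. The plan's own examples.** With treatment start 20OCT2001, coding Tables 4-3 and 4-4 as written reproduces all seven rows of Table 4-5:
- year missing: blank
- year 2000: 01JUL2000 (D)
- year 2002: 01JAN2002 (E)
- year 2001: 21OCT2001 (B)
- SEP2001: 15SEP2001 (C)
- OCT2001: 21OCT2001 (B)
- NOV2001: 01NOV2001 (A)

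**2. Which rule applies in the switch month.** The earliest switch in the Visit 10 window, Day 77, is 76 days after treatment start. No calendar month exceeds 31 days, so the switch month is always later than the start month and rule (A) applies. Enumerating all 1,461 start dates from 2014 to 2017 (an illustrative calendar, each date equally likely), with DFX starting on Day 77, 84, 85 or 91, gives rule (A) in 1,461 of 1,461 each time.

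**3. Example.** First EPO dose 20OCT2001; DFX on Day 85 = 20OCT2001 + 84 days = 12JAN2002. An AE recorded as JAN2002 becomes 01JAN2002, which is Day 74, 11 days before DFX.

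**4. How often the imputed date precedes DFX.** It equals the DFX date only if DFX starts on the 1st: 4 years × 12 months = 48 of 1,461 = 3.3%. Otherwise it is earlier: 1,413/1,461 = 96.7%.

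**5. How often that is wrong.** Take a month of L days, DFX on day s, and onset uniform over the month. The share starting on or after DFX but dated before it, averaged over s, is

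Σ(s=2..L) [(L − s + 1)/L] × (1/L) = (L − 1)/(2L).

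For L = 30 this is 29/60 = 0.483; for L = 31, 30/62 = 0.484. The enumeration gives 48.4%. The share truly starting before DFX is Σ(s=2..L) [(s − 1)/L] × (1/L), also (L − 1)/(2L), about 48%. The remaining 3% or so is DFX starting on the 1st.

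**6. The same event in the combination arm.** If 12JAN2002 is the first dose of EPO+DFX, JAN2002 meets rule (B), becomes 13JAN2002 and is kept.

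**7. Whether it leaves weeks 13-24.** SAP 2.10.2 does not say whether week 13 begins at the first DFX dose or on a fixed day.
- Begins at first DFX dose: the event falls before the period in 96.7% of start dates.
- Fixed Day 85: before the period in 100% (DFX on Day 77 or 84), 96.7% (Day 85) and 77.0% (Day 91). In the last case 7 × 48 = 336 of 1,461 = 23.0% stay in.

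**The case against.** **Few events should be affected.** SAP 4.3 wants partial dates caught by edit checks and returned to the investigator, and Protocol 9.4 requires queries for missing values. AEs are sought at every visit, and visits after the first month are about 4 weeks apart. Only the non-responding part of roughly 30 EPO patients (60 randomised 1:1) can switch. This stands: the effect is probably small.

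**The programming detail is elsewhere.** SAP 1.1 defers imputation specifications to Module 8, which is not available, and SAP 4.3 does not cite 4.2.2 for its reference date. This stands in part. However, no other definition of treatment start is offered, and 4.3 prints the algorithm as the rule.

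**The present rule is right about as often as it is wrong.** This stands. Step 5 gives about 48% each way, so a change alters the direction of error, not its frequency.

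Three stronger readings might be inferred, and the documents do not support them:
- *The event is lost, or charged to EPO.* It stays treatment-emergent and is listed with its partial date. The first bullet of SAP 2.10.2 does not make clear whether switchers' EPO phase enters the EPO weeks 1-12 table, so its destination cannot be determined.
- *Year-only dates always leave the DFX period too.* Under rule (E) this needs a switch after 1 January. With first EPO 01SEP2014 and DFX on Day 85 (24NOV2014), an AE known only as 2015 becomes 01JAN2015, Day 123, inside weeks 13-24.
- *Serious hypersensitivity reactions would be hidden.* Protocol 8.2.2 requires SAEs within 24 hours, with relationship assessed for each study treatment. A missing day is least likely there.

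**Conclusion.** The point holds for month-only AE dates in the month a switcher starts DFX. Rule (A) dates them before the first DFX dose unless DFX starts on the 1st, and they can then drop out of the weeks 13-24 tables. Under uniform onset, about 48% of such AEs would truly have begun on DFX. For these dates the error has one direction: the rule can take a DFX-phase AE out of the DFX period but cannot bring an EPO-phase AE in. It also treats the two DFX-exposed groups differently.

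The conclusion assumes that the reference date in 4.3 is the one defined in 4.2.2 and that Module 8 adds no switch rule. The 48% is conditional on an unresolved partial date in that one month; it is not a share of all AEs. The documents give no count of such dates, so a reader could not conclude that the safety comparison is materially distorted. This is a small, correctable gap in a descriptive pilot.

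**What to change.** Keep Table 4-3 with its present reference date for all patients and add one exception. For switchers only, if the AE's known month and year equal those of the first DFX dose, and no other information (such as end date or visit of report) shows onset before that dose, impute first DFX dose date + 1. In the example, JAN2002 becomes 13JAN2002, Day 86. Add this as a row in Table 4-5.

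Do not rerun Table 4-3 with the DFX start as reference. OCT2001 would then meet rule (C) and become 15OCT2001, before the first EPO dose on 20OCT2001, and a treatment-emergent AE would become pre-treatment.

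State also that switchers' weeks 13-24 period begins at the first DFX dose. With a fixed Day 85, a Day 77 switch would give Day 78 under the exception and still miss the period.

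The cost is a short SAP addition, one example row and one programming rule. The downside should be named: under uniform onset about half of the AEs moved would truly have begun on EPO alone and would be counted in the DFX period. That is the conservative direction rule (B) already takes, and the listings keep the partial date. No dose or clinical rule changes.
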